6.4. Randomization and Blinding

This is an open-label study.

7. STUDY POPULATION

7.1. Target Population

Approximately 48 adult male and female subjects with cGVHD will be enrolled. Subjects will be eligible for enrollment as defined by the following inclusion and exclusion criteria.

7.2. Inclusion Criteria

The inclusion criteria are detailed below:

1. Adult male and female subjects at least 18 years of age who have had allogenic bone marrow transplant or hematopoietic stem cell transplantation.
2. Receiving glucocorticoid therapy and calcineurin therapy or glucocorticoid therapy alone for cGVHD at study entry. Subjects on calcineurin therapy only, without glucocorticoid therapy, are not eligible. Subjects also receiving other therapies thought not to be immunosuppressive (such as extracorporeal photopheresis [ECP]), will be considered for enrollment in this study on a case-by-case basis.
3. Have persistent active cGVHD manifestations, as defined by 2014 NIH Consensus Development Project on Criteria for Clinical trials in cGVHD, after at least 2 months of steroid therapy.
4. No more than 3 prior lines of treatment for cGVHD.
5. Karnofsky Performance Scale of > 40 (see [Appendix E](#)).
6. Adequate organ and bone marrow functions evaluated during the 14 days prior to enrollment as follows:
 - a. Absolute neutrophil count $\geq 1.5 \times 10^9/L$ (without myeloid growth factors within 1 week of study entry)
 - b. Platelet count $\geq 50 \times 10^9/L$ (without transfusion or thrombopoietin or thrombopoietin analogues within 2 weeks of study entry)
7. Adequate safety laboratory values:
 - a. Total bilirubin $\leq 1.5 \times$ upper limit of normal (ULN)

- b. ALT and AST $\leq 3 \times$ ULN
 - c. Glomerular filtration rate (GFR) ≥ 30 mL/min/1.73 m² using the 4-Variable Modification of Diet in Renal Disease (MDRD-4) variable formula (see [Appendix F](#))
8. Female subjects of childbearing potential have a negative pregnancy test at screening. Females of childbearing potential are defined as sexually mature women without prior hysterectomy or who have had any evidence of menses in the past 12 months. However, women who have been amenorrheic for 12 or more months are still considered to be of childbearing potential if the amenorrhea is possibly due to prior chemotherapy, anti-estrogens, or ovarian suppression.
9. Women of childbearing potential (ie, menstruating women) must have a negative urine pregnancy test (positive urine tests are to be confirmed by serum test) documented within the 24-hour period prior to the first dose of study drug.
10. Sexually active women of childbearing potential enrolled in the study must agree to use 2 forms of accepted methods of contraception during the course of the study and for 3 months after their last dose of study drug. Effective birth control includes:
- a. Intrauterine device plus 1 barrier method;
 - b. Stable doses of hormonal contraception for at least 3 months (eg, oral, injectable, implant, transdermal) plus one barrier method;
 - c. Two barrier methods. Effective barrier methods are male or female condoms, diaphragms, and spermicides (creams or gels that contain a chemical to kill sperm); or
 - d. A vasectomized partner
11. For male subjects who are sexually active and who are partners of premenopausal women: agreement to use 2 forms of contraception as in Criterion #10 above during the treatment period and for at least 3 months after the last dose of study drug.
12. Able to provide written informed consent prior to the performance of any study-specific procedures.

7.3. Exclusion Criteria

The exclusion criteria are detailed below:

1. Female subject who is pregnant or breastfeeding.
2. Receiving an investigational GVHD treatment within 28 days of study entry.
3. Has acute GVHD.
4. Taking any medication known to be a moderate or strong inhibitor of the CYP3A4 isozyme or any drugs that are moderate or strong CYP3A4 inducers (see [Appendix H](#)).
5. History or other evidence of severe illness or any other conditions that would make the subject, in the opinion of the investigator, unsuitable for the study (such as poorly controlled psychiatric disease or coronary artery disease).
6. Regular and excessive use of alcohol within the 6 months prior to study entry defined as alcohol intake > 14 drinks per week in a man or > 7 drinks per week in a woman. Approximately 10 g of alcohol equals one “drink” unit. One unit equals 1 ounce of distilled spirits, one 12-ounce beer, or one 4-ounce glass of wine.
7. Known history of human immunodeficiency virus (HIV) or active hepatitis C virus (HCV) or hepatitis B virus (HBV).
8. Diagnosed with another malignancy (other than malignancy for which transplant was performed) within 3 years of enrollment, with the exception of completely resected basal cell or squamous cell carcinoma of the skin, resected in situ cervical malignancy, resected breast ductal carcinoma in situ, or low-risk prostate cancer after curative resection.
9. Relapse of the underlying cancer or post-transplant lymphoproliferative disease at the time of screening.
10. Has had previous exposure to KD025 or known allergy/sensitivity to KD025 or any other ROCK2 inhibitor.
11. Taking other immunosuppressant drugs for GVHD, including mammalian target of rapamycin (mTOR) inhibitors (Note: Only steroids, CNIs, and ECP are acceptable).
12. QTcF > 450 msec

8. STUDY ASSESSMENTS

8.1. Overview

The timing for these study assessments is presented in [Table 1](#), while a listing of clinical laboratory parameters to be measured is presented in [Section 8.8](#).

8.2. Screening Period (Day -29 to -1)

Informed consent must be obtained before any study-specific samples are taken or study-specific tests or evaluations are conducted. The following assessments at the screening visit are to occur within 28 days of first dose of study drug. Study eligibility will be based on satisfying all of the study inclusion and exclusion criteria.

At the screening visit, information will be collected and subjects will have clinical evaluations as follows:

- Informed consent
- Medical history and demographic data
- Complete PE, including height and weight
- Seated vital sign measurements (sitting blood pressure, pulse, respiratory rate, temperature)
- Karnofsky Performance Scale score
- Clinical laboratory tests (hematology and serum chemistry panel)
- Thyroid stimulating hormone (TSH)
- Urinalysis
- Virology (HBV, HCV, and HIV)
- Supine 12-Lead ECG; to be performed 3 times consecutively within 30 minutes (must have an interval of at least 1–2 minutes between ECGs); perform ECG immediately prior to blood sample collection, if possible
- Urine pregnancy test (for women of childbearing potential. Positive results are to be confirmed with serum testing.)
- Concomitant medications assessment
- AE assessment

8.3. Enrollment

After completion of screening procedures and confirmation of subject eligibility, the subject will be enrolled into the study. Subjects who are enrolled into the study are to undergo all subsequent evaluations required by the protocol.

8.4. Treatment Period

8.4.1 Cycle 1, Day 1 (Baseline)

At the Cycle 1 Day 1 visit, subjects will come to the clinic to have the following procedures completed. (Note that if screening assessments are done within 14 days prior to Cycle 1 Day 1, they do not need to be repeated on Day 1).

- Complete PE, including weight
- Seated vital sign measurements (sitting blood pressure, pulse, respiratory rate, temperature)
- Karnofsky Performance Scale score
- Clinical laboratory tests (hematology and serum chemistry panel)
- Supine 12-Lead ECG (to be obtained 4 hours post-morning dose; to be performed 3 times consecutively within 30 minutes [must have an interval of at least 1–2 minutes between ECGs]; perform ECG immediately prior to blood sample collection, if possible)
- Urine pregnancy test (for women of childbearing potential. Positive results are to be confirmed with serum testing.)
- Pulmonary function tests (including forced expiratory volume in 1 second [FEV₁], forced vital capacity [FVC], diffusing capacity of carbon monoxide [DL_{CO}], total lung capacity [TLC], and residual volume [RV])
- PK sample collection (pre-dose [Time 0], and 1, 2, 3, 4, 5, and 6 hours after dosing [after first dose for subjects in the BID group])
- PD blood sample collection (pre-dose)
- Study drug administration
- Dispense study drug
- Dispense study drug diary
- Physician-Reported Global cGVHD Activity Assessment
- cGVHD Activity Assessment - Patient Self Report

- Lee cGVHD Symptom Scale
- Concomitant medications assessment
- AE assessment

8.4.2 Cycle 1, Days 8, 15, and 22 (± 3 days)

On Days 8, 15, and 22 of Cycle 1, subjects will come to the clinic to have the following procedures completed:

- Complete PE, including weight
- Seated vital sign measurements (sitting blood pressure, pulse, respiratory rate, temperature)
- Karnofsky Performance Scale score
- Clinical laboratory tests (hematology and serum chemistry panel)
- Study drug administration
- Collect study drug diary
- Concomitant medications assessment
- AE assessment

8.4.3 Cycles 2 and Beyond, Day 1 (± 3 days)

On Day 1 of Cycles 2 and beyond, subjects will come to the clinic to have the following procedures completed:

- Complete PE, including weight
- Seated vital sign measurements (sitting blood pressure, pulse, respiratory rate, temperature)
- Karnofsky Performance Scale score
- Clinical laboratory tests (hematology and serum chemistry panel)
- TSH
- Urinalysis
- Supine 12-Lead ECG; pre-dose on Day 1 of Cycle 4 and Cycle 7 only; to be performed 3 times consecutively within 30 minutes (must have an interval of at least 1–2 minutes between ECGs)
- Urine pregnancy test (for women of childbearing potential. Positive results are to be confirmed with serum testing.)

- Pulmonary function tests (including FEV₁, FVC, DL_{CO}, TLC, and RV; to be performed every other cycle, starting with Cycle 3 for subjects without lung involvement)
- PK sample collection (Cycle 2 only at the following time points: pre-dose [Time 0], and 1, 2, 3, 4, 5, and 6 hours after dosing [after first dose for subjects in the BID group]); a pre-dose sample is to be collected at the Cycle 4 and Cycle 7 visit
- PD blood sample collection (Cycles 2, 4, and 7 only: pre-dose)
- Study drug administration
- Dispense/Collect study drug
- Collect study drug diary
- Response assessment.
- Physician-Reported Global cGVHD Activity Assessment
- cGVHD Activity Assessment - Patient Self Report
- Lee cGVHD Symptom Scale
- Concomitant medications assessment
- AE assessment

At Cycle 25, Day 1 (C25D1), and all odd cycles thereafter (i.e., C27D1, C29D1, C31D1, etc.), subjects will receive 2 cycles worth of study drug along with 2 diaries and will return to the clinic at the next odd cycle for assessments and IP accountability. Investigators and/or subjects have the option of coming into clinic at one or more even cycles (i.e., C26D1, C28D1, C30D1, etc). On even cycles, when patients do not come to clinic, the study staff will contact the patient via phone and document any new adverse events and concomitant medications.

8.5. End of Treatment (EOT)

Subjects are to return to the study site within 3 days after the subject's last dose of study drug to complete all EOT assessments. This may occur at the visit at which disease progression is diagnosed. The following procedures will be completed:

- Complete PE, including weight
- Seated vital sign measurements (sitting blood pressure, pulse, respiratory rate, temperature)
- Karnofsky Performance Scale score
- Clinical laboratory tests (hematology and serum chemistry panel)

- TSH
- Pulmonary function tests (including FEV1, FVC, DLCO, TLC, and RV)
- Response criteria assessment
- Physician-Reported Global cGVHD Activity Assessment
- cGVHD Activity Assessment - Patient Self Report
- Lee cGVHD Symptom Scale
- Concomitant medications assessment
- AE assessment

8.6. 28-Day Follow-Up Visit

The Follow-Up visit will occur 28 (\pm 7) days after the last dose of study drug, but prior to starting on a new therapy (if a new therapy is started earlier). Subjects will return to the clinic and the following procedures will be completed:

- Complete PE, including weight
- Seated vital sign measurements (sitting blood pressure, pulse, respiratory rate, temperature)
- Karnofsky Performance Scale score
- Clinical laboratory tests (hematology and serum chemistry panel)
- TSH
- Urinalysis
- Supine 12-lead ECG; to be performed 3 times consecutively within 30 minutes (must have an interval of at least 1–2 minutes between ECGs); perform ECG immediately prior to blood sample collection, if possible
- Urine pregnancy test (for women of childbearing potential. Positive results are to be confirmed with serum testing.)
- Concomitant medications assessment
- AE assessment

8.7. Unscheduled Visits

For subjects requiring an unscheduled visit, the following assessments may be performed at the investigator's discretion:

- Complete PE, including weight
- Seated vital sign measurements (sitting blood pressure, pulse, respiratory rate, temperature)
- Karnofsky Performance Scale score
- Clinical laboratory tests (hematology and serum chemistry panel)
- TSH
- Urinalysis
- Supine 12-Lead ECG; to be performed 3 times consecutively within 30 minutes (must have an interval of at least 1–2 minutes between ECGs); perform ECG immediately prior to blood sample collection, if possible
- Urine pregnancy test (for women of childbearing potential. Positive results are to be confirmed with serum testing.)
- Pulmonary function tests (including FEV₁, FVC, DL_{CO}, TLC, and RV)
- Collect study drug (if appropriate)
- Collect study drug diary (if appropriate)
- Physician-Reported Global cGVHD Activity Assessment
- cGVHD Activity Assessment - Patient Self Report
- Lee cGVHD Symptom Scale
- Concomitant medications assessment
- AE assessment

8.8. Long-Term Follow-Up

Subjects will be contacted approximately every 8 weeks and can be contacted via telephone, email or postal mail to confirm survival status and the initiation of any anti-cancer treatment or any changes in treatment of cGVHD. This can also be confirmed from electronic medical records.

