17.4. Activity Analysis

The primary activity outcome will be the percentage of subjects who meet the OR criteria (PR + CR). This will be assessed overall (ie, any subject meeting the PR or CR criteria at any time point). For clarity, addition of new systemic therapy for cGVHD will be considered a KD025 treatment failure and will be considered progression of cGVHD for analysis purposes.

Secondary Endpoints

- Number and percentage of KD025 in subjects with steroid-dependent cGVHD who have a best response of PR or CR
- Change in cGVHD severity as based on the Physician-reported Global cGVHD Activity Assessment
- Change in symptom activity as based on cGVHD Activity Assessment Patient Self-Report
- Median FFS will be defined as the time from first dose of study drug to either the start of another treatment, relapse of the underlying disease, or death.
- Changes in corticosteroid and calcineurin inhibitor dose
- To evaluate DOR, which will be defined as the time of initial response until documented progression.
- To evaluate response by organ system. The response by organ system (PR and CR) will be assessed based on the 2014 NIH Consensus Development Project on Clinical Trials in cGVHD.
- Analyses of plasma PK of KD025 in subjects with cGVHD
- OS will be defined as the time from first dose of KD025 to the date of death due to any cause. Kaplan-Meier plots, descriptive statistics of OS and landmark OS at 6, 12, 18 and 24 months will be provided.
- TTNT will be defined as the defined as the time from the first dose of KD025 to the start of additional systemic cGVHD therapy Change in symptom burden/bother using the Lee cGVHD Symptom Scale.

Exploratory Endpoints

- Changes in the expression of several cytokines (including IL-17A, IL-21, and IL-2) in plasma after KD025 administration to subjects with cGVHD
- Changes in percentage of immune-cell subtypes (including Th17 and Treg cells) in whole blood after KD025 administration to subjects with cGVHD

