## **2.2 Study Design**

This is a Phase 2a, open-label, dose-escalation, safety, tolerability, and activity study.

Subjects who have signed an Institutional Review Board/Independent Ethics Committee-approved informed consent form and who have met all of the inclusion/exclusion criteria will be enrolled. After approximately 4 weeks for screening, subjects will receive KD025 orally (PO) in 28-day cycles until disease progression or unacceptable toxicity occurs followed by 4 weeks of follow-up. In addition, subjects will be contacted every 8 weeks until study close-out to confirm survival status and the initiation of any anticancer treatment or any changes in treatment for cGVHD.

Sequential cohorts of approximately 16 subjects will be dosed at KD025 200 mg once daily (QD) PO, KD025 200 mg twice daily (BID) PO, and KD025 400 mg QD (Table 1). Prior to enrolling subsequent cohorts, the safety data in each previous cohort will be evaluated after 8 subjects have reached 2 months of treatment.

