### **3.8.2.7 Failure-free Survival (FFS)**

Failure-free survival will be defined as the time from first dose of study drug to either the start of another new systemic treatment for cGVHD, relapse of the underlying

disease (both will be defined by clinical team review), or death. If no such events happen, FFS will be censored by last response assessment or long term follow up assessment, whichever is the latest and available. Failure-free survival will be analyzed by the Kaplan-Meier survival method as well as the landmark analyses at 6, 12, 18, and 24 months. In addition, analyses for the three components of FFS will also be provided.

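### Relapse is a failure event in FFS, but the long-term follow-up contact at which FFS is censored does not ask about it, so FFS can be overstated

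*Protocol*

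**What the plan says.** Protocol 17.4 measures FFS from first dose "to either the start of another treatment, relapse of the underlying disease, or death". SAP 3.8.2.7 narrows the treatment component, so that the event is "either the start of another new systemic treatment for cGVHD, relapse of the underlying" "disease (both will be defined by clinical team review), or death". A subject with none of these is handled as follows: "FFS will be censored by last response assessment or long term follow up assessment, whichever is the latest and available". The SAP plans Kaplan-Meier estimates, landmarks at 6, 12, 18 and 24 months, and separate analyses of the three components. SAP Table 5 lists a table and a figure with cumulative failure rates by component, and a listing of failure events.

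On data collection, Protocol 8.8 states: "Subjects will be contacted approximately every 8 weeks". The contact is made "to confirm survival status and the initiation of any anti-cancer treatment or any changes in treatment of cGVHD", and the protocol allows this to be confirmed from medical records instead. The same content appears in the protocol synopsis, section 6.3 and Table 1 footnote m. SAP 2.2 agrees: "to confirm survival status and the initiation of any anticancer treatment or any changes in treatment for cGVHD". None of these places lists relapse or its date.

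**The concern.** Censoring at a contact is sound only if the status of every failure component is known at that contact. Here two of the three components, death and new cGVHD treatment, are asked about directly. The third has only a proxy, the start of anti-cancer treatment. Followed as written, the plan credits relapse-free time up to a date at which nobody had to ask about relapse.

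At stake are the FFS curve and landmarks, which would look better than they should, and the component analysis. In the latter, relapse would be understated and some relapses would appear as deaths without relapse. The landmarks run to 24 months, so much of the relevant time may fall after treatment has ended for subjects who stop early.

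**Working it through.** **Step 1: set the endpoint against the data collected beyond 28 days after last dose.**

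| FFS component (SAP 3.8.2.7) | Asked at the long-term contact? | What reaches the reviewers |
|---|---|---|
| Death | Yes | Survival status |
| New systemic cGVHD treatment | Yes | Changes in cGVHD treatment |
| Relapse | No | Start of anti-cancer treatment only |

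Response assessments stop at the end-of-treatment visit (Protocol Table 1), and routine adverse event recording stops 28 days after last dose (Protocol 16.2). After that, the long-term contact is what moves the censoring date forward.

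**Step 2: follow a relapse in that period.**

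- No anti-cancer treatment, subject alive at last contact: censored as failure-free after relapsing.
- No anti-cancer treatment, subject dies: counted at death, as a death.
- Anti-cancer treatment given: the contact supplies a treatment start. Under the SAP wording that treatment is not itself an FFS event, so relapse has to be inferred from it. The event can then be dated at treatment start. The SAP's rule for missing event dates applies only when the day is missing, so it does not help if the month of relapse is unknown.

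In each case the recorded failure time is the same as or later than the true one. The curve being estimated therefore lies at or above the true FFS curve. In a small sample with censoring, a single late-dated event need not raise the Kaplan-Meier estimate at every later time, but nothing in this mechanism moves a failure earlier.

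**Step 3: size when the relapse is never recorded.** The documents state no FFS rate, relapse rate or share of relapses left untreated, so there is no plan figure to reproduce and the inputs are assumptions. Let S(t) be true FFS with a constant hazard, r the share of failures that are relapses, and m the share of all relapses that go unseen. Removing the unseen part of the hazard gives

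S*(t) = S(t)^(1 − rm).

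This assumes that a subject with an unseen relapse goes on to fail from other causes at the usual rate. Assumed ranges: S(12 months) 40-60%, r 5-20%, m 10-50%.

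- Smallest at 12 months: 0.60^(1 − 0.05×0.10) = 0.60^0.995 = 0.6015, or +0.15 (about 0.2) points.
- Central: 0.50^(1 − 0.10×0.25) = 0.50^0.975 = 0.509, or +0.9 points. The median moves from 12.0 to 12.0/0.975 = 12.3 months.
- Largest at 12 months: 0.40^(1 − 0.20×0.50) = 0.40^0.90 = 0.438, or +3.8 points.
- At 24 months, with S(24) = S(12)²: from 0.16^0.995 = 0.161 (+0.1 points) to 0.36^0.90 = 0.399 (+3.9 points).

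**Step 4: size when the relapse is found only at death.** This was simulated with an exponential lag from relapse to death and a true 12-month FFS of 50%.

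- r = 10%, m = 25%, mean lag 3 months: 49.9% becomes 50.2%.
- r = 10%, m = 50%, mean lag 6 months: 50.0% becomes 50.9%.
- r = 20%, m = 50%, mean lag 6 months: 50.1% becomes 52.0%.

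The overstatement is therefore about 0.3 to 2 points.

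**Step 5: weight of one subject.** With nobody censored before the landmark, one missed relapse moves FFS by at most 1/16 = 6.3 points in a cohort, or 1/48 = 2.1 points overall. It moves it by nothing if that subject has failed in another recorded way by the landmark.

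**The case against.** The strongest reply is that the protocol does intend to collect FFS data. Section 10.4 says so for the whole study, section 8.8 permits use of medical records, and SAP 3.8.2.7 gives the identification of relapse to clinical team review. The case report form is not among the documents and may already hold a relapse field. This stands against any claim that relapses are certain to be lost. It does not close the gap. Section 10.4 names no item or date, the records option refers back to the same listed items, and the SAP does not say what data the team will review.

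A reader might go further and infer from the absence of a relapse row in Table 1 that relapse is also uncollected during treatment, or that an untreated relapse is never recorded at all. The documents do not support that. Protocol 9.1 has FFS evaluated at the same time points as the activity assessments, which are Day 1 of each cycle and end of treatment. Sections 16.2 and 16.3.7 require untoward events through 28 days after last dose to be recorded with onset dates, and nothing exempts relapse. SAP 3.9.1 has the investigator relate adverse events to the underlying disease. The gap is confined to the later period.

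It is also fair that the subjects whose relapse is missed altogether are few: more than 28 days off drug, alive, with neither new systemic cGVHD therapy nor anti-cancer treatment. Sampling error is far larger: an exact 95% interval for 8 of 16 runs from about 25% to 75%. That bears on importance. Even so, this error runs in one known direction and can be prevented.

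**Conclusion.** The point holds for follow-up beyond 28 days after last dose. There the plan defines relapse as a failure, does not list it among the things to be asked, and censors at the contact where it was not asked. FFS can be overstated and its relapse component understated.

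The overstatement at 12 months is about 0.2 to 3.8 points, or 0.9 in the central case. It rests on assumed FFS, relapse and ascertainment rates and on constant hazards. Because m is a share of all relapses, those recorded during treatment keep it low. The figures of 6.3 and 2.1 points might be read as the expected bias, but they are only the weight of one subject.

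FFS is a secondary, descriptive endpoint with no planned comparison or power claim, and the primary overall response rate is unaffected. This is a worthwhile and inexpensive correction, and it does not threaten the study's main result.

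**What to change.** 1. Add one item, relapse of the underlying malignancy (yes/no, date of relapse), to the long-term follow-up contact in Protocol 8.8, and repeat it in Table 1 footnote m, section 6.3, the synopsis and SAP 2.2.
2. For subjects already in long-term follow-up, collect the same item retrospectively from medical records, a source that 8.8 already allows.
3. In SAP 3.8.2.7, state that clinical team review of relapse uses this item together with the on-treatment adverse event records, and that the event is dated at relapse and not at the start of anti-cancer treatment.

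The cost is one more question at a contact already being made and one case report form field, plus the record check for subjects already in follow-up. No visit or procedure is added, and no new cycle-visit field is needed, because on-treatment relapse falls under the existing FFS evaluation and adverse event recording.
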